6.6.2 Human Tissue Samples *6.6.2.1* Blood

15ml of whole blood will be taken for safety at baseline, 12 and 24 weeks post-randomisation. These may be taken and processed at the recruiting site.

15ml of whole blood for research purposes will be taken at baseline, 12 and 24 weeks postrandomisation at the recruiting site where possible. Where study visits are conducted remotely, patients will receive a home-kit for collection of a blood sample from a finger prick using a dried blood spot sample card and they will return it by post to Bioanalytical facility, Bob Champion Research and Education Centre. However, it may not be possible to obtain samples from all participants at any or both timepoints. Zero, one or both research blood samples will be obtained from participants willing to provide samples for analysis in future research projects.

If participants are willing, we will also ask to take an additional blood sample of 15ml for research purposes, which will be analysed in future ethically approved studies. This may include genetic analysis if the participants consent to this. These samples will be stored at the Norwich Research Park Biorepository at the end of the study.

6.6.2.2 Urine

NCTU_O_TaT_7_v4.0_ProtocolTemplate *PUFFIN Trial Protocol v1.5 24/08/2023* IRAS number: 1004006 Participants will be asked to provide a urine sample for research purposes at screening, baseline and at 24 weeks post randomisation. For consistency the baseline and screening samples should be collected at the same time of day.

Screening sample

The participant will be asked to collect a sample ideally between 8-10am which will be transported to the Bioanalytical facility, Bob Champion Research and Education Centre, Norwich Medical School direct from the participants home or via the hospital.

Baseline and 24 weeks post-randomisation sample

Ideally the sample should be of the second elution of the day collected between 0800 and 1000 on the day of the study visit as previously described(35) although, as there is no evidence of diurnal variation(36), the timing of the sample is not crucial. However, sample collection should be the same time of day for both the baseline and 24 week samples. Ideally sample collection should be undertaken in the morning at the hospital clinic/research facilities but if that is not possible it can be collected at an afternoon study visit. The sample will then be aliquoted into 3 x 1ml pre-labelled vials and stored at -80 C before batch shipping on dry ice to the Bioanalytical facility, Bob Champion Research and Education Centre.

6.6.2.3 Sputum

Sputum will be collected, processed and analysed according to the sputum laboratory manual. In brief, induced sputum will be collected as previously described(31) after inhalation of increasing concentrations of hypertonic saline if possible. Sputum will be processed as described by Pizzichini et al(32). The sputum plugs will be selected from saliva, processed with dithiothreitol (DTT) and centrifuged. Supernatants will be stored at -80°C for analysis of SPM. Total cell count will be calculated and cell viability determined. Cytospins will be prepared and stained by Wright's stain for differential cell count. For SPM, sputum samples will be acidified, applied to solid-phase extraction cartridges and the eluted SPM will be analysed by liquid chromatography–tandem mass spectrometry as previously described(34). This analysis will be undertaken by trained technicians in centres with experience of undertaking, or capacity to undertake, this analysis for clinical research.

6.6.2.4 Storage and transportation

The lab manual will provide further details of sample handling and storage at recruiting sites, and transported to the Bioanalytical facility, Bob Champion Research and Education Centre for analysis then storage at Norwich Research Park Biorepository for future analysis of any potential biomarker including but not limited to N-ERD, asthma, or nasal disease pending additional ethical approval, at a later date.

Sample handling training will be provided to all sites prior to activation detailing sample collection, handling and storage procedures. Detailed written instructions and appropriate tissue transfer agreements will be put in place prior to the transfer of relevant material.

6.6.3 Early Stopping of Follow-up

Sites must inform NCTU of all forms of early trial discontinuation via the eCRF. In instances where a participant has decided to withdraw consent, it is essential for the site to establish which aspects of the trial the participant is withdrawing consent from.

- If a participant chooses to discontinue their trial treatment, they should continue to be followed up as closely as possible to the follow-up schedule defined in the protocol, providing they are willing. They should be encouraged and facilitated not to leave the whole trial, even though they no longer take the trial treatment.
- If, however, the participant exercises the view that they no longer wish to provide data either through study visits or remotely via the registry, this view must be respected, and the participant withdrawn entirely from the trial. Data already collected will be kept and included in analyses according to the intention-to-treat principle for all participants who stop follow up early. Any samples provided by the participants, which have yet to be analysed will be destroyed and the registry will be updated so that no further data is provided to NCTU.

Where patients are unable or unwilling to continue to undertake study measurements/activities, the decision as to whether the participant should continue with trial treatment and/or follow-up assessments will be at the discretion of the local PI and/or CI.

Participants who stop trial follow-up early will not be replaced.

6.6.4 Participant Transfers

If a participant moves from the area making continued follow-up at their consenting centre inappropriate, every effort should be made for them to be followed-up at another participating trial centre. Written consent should be taken at the new centre, either electronically or paper-based following consultation either in person or via video/phone call, and then a copy of the participant's CRFs should be provided to the new centre. Responsibility for the participant remains with the original consenting centre until the new consent process is complete.

6.6.5 Loss to Follow-up

Sites will be asked to account for the vital status and details of admission to hospital for all patients who have consented to participate in the study regardless of whether they have withdrawn from the intervention or study assessments.

6.6.6 Trial Closure

The end of the trial is defined as 4 months following the last follow-up visit of the last patient randomised, to allow for data entry and data cleaning activities to be completed.

6.7 Sample Size

The primary outcome will be the change in asthma control questionnaire (ACQ-6) mean score. This has a standard deviation (SD) of 0.67(37) and a minimal important difference of 0.5(38). Assuming a 20% withdrawal rate, we will have 90% power at the 0.05 significance level to detect a change in our primary outcome if we randomise 98 individuals into the study. Assuming a 30% withdrawal rate, a sample of 52 patients will provide 80% power to detect a 15% reduction in absolute sputum eosinophil count(39). The DMC will monitor the assumptions of the sample size calculation in accordance with the Terms of Reference.

6.8 Recruitment and Retention

6.8.1 Recruitment

Patients will be identified from review of patient registries, hospital medical records and databases of research interested patients or clinical details as well as those who self-refer. However, many people with N-ERD are undiagnosed as the proportion of people with N-ERD recorded in clinical records do not equate to detailed studies. Targeted screening of people with a high probability of a diagnosis of N-ERD is permitted within the protocol. The screening and recruitment strategies, summarised in figure 3, may include any of the following:

- Patients with asthma and a clear diagnosis of N-ERD based on a previous positive nasal, inhaled or oral aspirin challenge undertaken for clinical or research reasons will be considered to have a **clear diagnosis** of N-ERD and will meet this eligibility criteria for participation in the study.
- Patients with more than one reaction to NSAIDs plus history of nasal polyposis or asthma will be considered to have a **clear diagnosis** of N-ERD and will meet this eligibility criteria for participation in the study.
- Patients with a single reaction to a NSAID or aspirin plus a history of nasal polyposis plus moderate or severe asthma, defined as, asthma at least "additional-add on therapy" as defined by the BTS/SIGN158 British guidelines on the management of asthma (https://www.brit-thoracic.org.uk/quality-improvement/guidelines/asthma), and one the following criteria will be considered to have a clear diagnosis of N-ERD and will be invited to participate in the study.
- Patients with a history of nasal polyposis plus asthma plus blood eosinophilia (≥300x106/L) or raised FeNO (>25ppb) within last 12 months will be considered to have a high probability N-ERD and will be enrolled in the study if they have a uLTE4/Creatinine concentration of greater than 800pg/mg(35, 40).
- Patients with asthma and a history of nasal polyposis will be considered to have a high probability of N-ERD and can be enrolled into the study if they have a uLTE4/Creatinine concentration of greater than 350 pg/mg up and a positive nasal aspirin challenge as described below.

Nasal aspirin challenge will be modified from the published version of the aspirin challenge(41) to reduce the dose steps as this is appropriate for a screening test for the purpose of this study. One sachet (500mg) of lysine aspirin will be dissolved in 10 ml saline. Peak nasal inspiratory flow or acoustic rhinometry plus evaluation of upper and lower respiratory tract symptoms will be undertaken before and 10 minutes after nasal instillation of saline and 45 minutes after nasal instillation of 15mg (0.15ml in each nostril) lysine aspirin followed by 30mg (0.3ml each nostril) then 100mg (1ml in each nostril) of lysine aspirin. The test will be considered positive at any stage if there are symptoms plus a greater than 25% reduction in nasal volume or a 50% reduction in peak nasal inspiratory flow. If this occurs post saline the subject is hyper-reactive and the test should be stopped and re- performed once better control of upper airway inflammation is achieved.

Patients will be approached by the clinical care team, by way of any of the following methods, if they have documented history of a clear diagnosis of N-ERD or high probability of N-ERD and will be invited to participate in the study and attend a screening visit to establish their suitability in terms of the other entry criteria. The clinic staff will arrange a subsequent screening visit.

- The clinic team may mail (by post or e-mail) an invitation letter with or without a participant information sheet along with a contact email address/phone number to respond to, detailing a range of methods for the interested potential patients to contact the local trial team to arrange a screening appointment.
- Where patients are due to attend clinic for a routine appointment in the near future, the clinical care team may mail (by post or e-mail) an invitation letter on hospital headed paper which provides an overview of the study, and a participant information sheet, so that the patient receives these documents at least 24 hours in advance of the forthcoming routine clinic assessment visit. After the participant has provided written informed consent, screening for eligibility and baseline assessments will be undertaken at the routine clinic visit.
- For centres with access to a volunteer database, the researchers may mail the invitation letter and reply form directly to the volunteer.

Figure 3: PUFFIN Identification and Recruitment Strategies

Potential patients may be contacted by phone between 3 and 7 days after the mailing of the letter/sending the email to ensure that they have received it. Enrolment will then be scheduled either via a face-to-face visit or by consultation via phone/video call for those willing to consent to participate. Potential participants and site staff will confirm whether consent will be recorded electronically or on paper, with the decision documented in the patient's medical notes, to facilitate preparations for the enrolment visit.

Remote consent

For those being enrolled remotely and completing paper consent forms, a localised consent form with a freepost or stamped address envelope, will be mailed to the potential participant for their completion following the study consultation. The person taking consent will countersign the form upon receipt at the recruiting site.

Where electronic consent is being sought, participants will verbally consent to the sharing of their email address and/or contact details in order to receive the link to the electronic consent form to facilitate the process. This will be documented by site staff in the patient's medical notes. Both parties will complete the electronic consent form following the phone/video call consultation by providing a wet-ink signature equivalent on the designated field via REDCap (49).

Details of the consultation, including but not limited to the time/date of the phone/video call, confirmation of identification checks and the name of the staff member leading the call and thus taking consent will be recorded in the patient's medical notes. Copies of the completed forms will be mailed (by post or email) to participants.

6.8.2 Retention

This study has been designed to be of a short duration and to utilise remote assessments wherever possible. It is intended that questionnaires are completed at home to minimise the time that the participants are in the hospital. In exceptional circumstances drug may be able to be couriered to the patients for convenience; however, this will need to be arranged via the NCTU Trial Team with approval from the CI. However, some of the study assessments require physiological measurements required to be undertaken in a clinical research facility or similar setting.

Participants will also be offered the option to subscribe to an email-based participant newsletter during the study's recruitment period in order to help keep participants engaged and informed of study progress during and beyond their participation.

Participants will be given/posted a card with the contact details of the local PI that will request details of hospital admissions to be reported at consent/baseline. Patients will be asked to provide informed consent for their contact details to be stored in a trial contacts database at UEA. Participants can withdraw consent to this in writing at any time.

6.9 Assignment of Intervention

6.9.1 Allocation

6.9.1.1 Sequence generation

The allocated treatment for a patient will be generated via computer written code using stratification. Stratification will be performed using the factors measured at baseline: i) study site, ii) participation in the sputum sub-study (yes/no)).

Full details of the stratification will be documented in a separate document (PUFFIN Allocation Schedule) stored in a shared file accessible to only the study statistician(s) and data management team as appropriate.

6.9.1.2 Allocation concealment mechanism

Allocation will be computer generated by a web-based system ensuring concealment prior to randomisation. Following consent and confirmation of eligibility the PI or delegate will enter data confirming eligibility into the eCRF generating a participant identification number. Blinded notification of randomisation will be sent to the PI and/or delegates, CI and NCTU trial team. A semi-blinded notification of randomisation will be sent to the site clinical trial pharmacy.

6.9.1.3 Allocation Implementation

The PI or delegated sub-investigator is responsible for ensuring only eligible patients are randomised and prescribed study medication. Patients will be allocated to the intervention by a process embedded in the web-based data management system. The randomisation code will be saved in the study database for later decoding and also for emergency unblinding purposes.

6.9.2 Blinding

This is a double-blind study. The placebo and active treatments will appear identical and will be dispensed in identical containers. All trial participants, care providers and outcome assessors will remain blind throughout the study.

6.9.3 Emergency Unblinding

The decision to unblind a single case should be made when knowledge of an individual's allocated treatment is required:

- To enable treatment of severe adverse event/s, or
- In the event of an overdose.

Where possible, requests for emergency or unplanned unblinding of individuals should be made via the trial manager and agreement of the CI will then be sought. However, in circumstances where there is insufficient time to make this request or for agreement to be sought, the treating clinician should make the decision to unblind immediately. This will be done via the study database (local PIs and the CI will have special logins which will allow unblinding and which will be closely audited within the database management system) or by contacting the CI who will authorise unblinding by the Data Management Team. All instances of unblinding should be recorded and reported to NCTU by the local PI, or delegate, including the identity of all recipients of the unblinding information.

6.9.4 Non-emergency Unblinding

For circumstances where non-emergency unblinding is required e.g. GP/clinician or participant request, following confirmation from the CI, treatment allocation will be revealed by the eCRF, using

logins and forms separate to those required to unblind in emergency situations. The blinding will be maintained for as many of the local study and NCTU trial team members as possible. A record of non-emergency unblinding and those individuals unblinded to trial treatment will be recorded and filed.

6.10 Data Collection, Management and Analysis

6.10.1 Data Collection Methods

An on-line patient screening log will contain the details of the patient initials, date of contact and the route of identification for all potential participants who have received a patient information sheet (PIS). Following confirmation of consent, each participant will be given a unique trial Participant IDentification Number (PID). Data will be collected at the time-points indicated in the Schedule of Assessments (see section 6.6).

Data collection will vary according to the data variable in question.

1) ACQ is recognised by the American Thoracic Society and NICE and widely used in research (http://www.qoltech.co.uk/index.htm). The ACQ-7 has seven items: five questions about symptoms, one about reliever inhaler usage and a measure of airflow. The five symptom questions enquiring are 1) woken at night by symptoms, 2) wake in the mornings with symptoms, 3) limitation of daily activities, 4) shortness of breath and 5) wheeze. Patients are asked to recall how their asthma has been during the previous week and to respond using a 7-point scale (0 = no impairment, 6 = maximum impairment). Clinic staff score the FEV1% predicted on a 7-point scale. ACQ-7 score is the mean of the 7 questions and therefore between 0 (totally controlled) and 6 (severely uncontrolled). The ACQ-7 is validated using FEV1 and although sometimes PEF is used in its place, this is not recommended. The ACQ-6 (ACQ-7 without lung function assessment) is also validated and reflects the weekly impact of asthma on the individual. We have chosen the ACQ-6 (symptoms and beta agonist usage) as this does not require measurement of spirometry, which is considered an aerosol generating procedure, and there is high agreement between the different versions of the ACQ (37). It will be measured every 6 weeks.

2) Asthma Quality of Life Questionnaire.

Mini Asthma Quality of Life Questionnaire (mini-AQLQ) will be measured at baseline, 12 weeks and 24 weeks. It is a 15-item questionnaire as is a short version of the complete 32-item questionnaire. It comprises four domains (symptoms, environment, emotions, activities) and assess the previous 2-week period. Scores range from 0-6 (lower is worse). The mini-AQLQ score is calculated as the average of domain items(26). The minimum clinically important difference is 0.5.

3) Health related quality of life.

The EQ-5D-5L(27) will be measured at baseline, 12 weeks and 24 weeks. It will be converted to utilities using standard UK health state valuations(42) and thence to Quality Adjusted Life Years (QALYs) gained by evaluation at multiple time-points and calculating the area under the curve over a 6-month period.

4) Airway calibre.

FEV₁ and FEF₅₀ will be obtained from spirometry, measured post-bronchodilator according to current American Thoracic Society/European Respiratory Society Taskforce guidelines(30). It will be measured at baseline, 12 weeks and 24 weeks (where possible). It will be reported as part of the ACQ-7 and as a

separate secondary outcome. The percentage predicted value will be taken from the reference values of the Global Lung Function Initiative (GLI) equations(43). All personnel undertaking this procedure will be accredited by the Association for Respiratory Technology & Physiology (ARTP) or will receive specific training at site initiation. Spirometry is considered to be the gold standard assessment of airway calibre and bronchoconstriction in airways disease and is fundamental in the assessment of patients with asthma. It is undertaken as part of routine clinical practice. Peak expiratory flow (PEF) will be measured every 6 weeks at home by the participants.

5) Peak nasal inspiratory flow (PNIF) is a method of assessing upper airway calibre. It will be measured by an In-Check Nasal Inspiratory Flow Meter (Clemment Clarke International Ltd, Harlow, UK). It correlates highly to nasal symptoms scores(44). It will be measured every 6 weeks at home (where possible).

6) FeNO will be measured, at baseline, 12 weeks and 24 weeks, using a NIOX MINO nitric oxide analyser (Aerocrine, Chicago, USA), according to the National Institute for Health and Care Excellence guidelines (www.nice.org.uk/guideance/dg12). It is used routinely in clinical care and recommended by NICE (NG80). FeNO is higher in people with N-ERD than aspirin tolerant asthma and increases to a significantly higher degree following aspirin challenge(45).

7) Urinary LTE4 and PGD2.

A urine sample will be collected at baseline and after 24 weeks of therapy and analysed by radioimmunoassay. uLTE4 reflects 4-series leukotriene pathway and is a biomarker for N-ERD. It will be corrected for urinary creatinine as this standard practice for this metabolite. PGD2 will also be measured using radioimmunoassay and will used to assess the cyclooxygenase pathway. PGD2 was also reduced significantly in the pilot study(46). See section 6.6.2.2 for details about sample collection, storage and transport.

8) Red blood cell fatty acid concentration (to assess adherence and fatty acid status - biological response relationships).

This will be measured at baseline, 12 weeks and 24 weeks. RBCs will be used as the blood lipid pool to assess habitual PUFA status at baseline and in response to intervention. In contrast to plasma fractions such as plasma cholesterol ester or triglycerides, which are variable and reflect recent intakes (last meal up to two weeks), RBC are a tissue which provide a marker of habitual intake in the few months(47) with less biological variability than plasma PUFA pools. For the RBC an increase of approximately 3.2-fold would be predicted following a 4g Omega-3 ethyl ester 90 dose(48). For the sensitivity analysis a 75% adherence cut-off will be used which equates to an RBC EPA+DHA enrichment of 2.7-fold.

9) The differential cell count and concentration of SPMs in sputum (subgroup of 52 patients at baseline and 24 weeks).

Induced sputum will be collected as previously described(31) after inhalation of increasing concentrations of hypertonic saline if possible. Sputum will be processed as described by Pizzichini et al(32). The sputum plugs will be selected from saliva, processed with dithiothreitol (DTT) and centrifuged. Supernatants will be stored at -80°C for analysis of SPM. Total cell count will be calculated and cell viability determined. Cytospins will be prepared and stained by Wright's stain for differential

cell count. For SPM, sputum samples will be acidified, applied to solid-phase extraction cartridges and the eluted SPM will be analysed by liquid chromatography–tandem mass spectrometry as previously described(34).

10) Blood eosinophils.

These will be measured, at baseline, 12 weeks and 24 weeks, in local clinical laboratories using coulter counters.

11) Full blood count, renal and liver function tests, and coagulation. These will be measured in local laboratories at baseline, 12 weeks and 24 weeks.

12) Urine pregnancy tests (WOCBP only) will be measured at baseline and 12 weeks.

13) Food frequency questionnaire (FFQ).

This will be performed at baseline, and 24 weeks using the validated European Prospective Investigation of Cancer (EPIC) FFQ(33), with the FFQ recognised as a robust methodology to capture habitual diet and is particularly suited to quantify foods not consumed on a daily basis, such as fish (main dietary source of EPA and DHA). The FFQ will be analysed using the online McCance and Widdowson's composition of foods integrated dataset, in order to establish habitual dietary intake; in particular, EPA and DHA.

14) Asthma attacks.

Asthma attacks will be defined as those resulting in death, hospitalisation, A&E attendance, out-ofhours medical contact, or a course or boost in oral corticosteroids (prednisolone) for asthma. The number of asthma attacks over the duration of the study will be captured.

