1.3 Structured trial summary

Primary Registry and Trial	
Identifying Number	
Date of Registration in Primary	
Registry	
Secondary Identifying Numbers	173-12-20
	1.5 12 20
Source of Monetary or Material	National Institute for Health and Care Research Efficacy and
Support	Mechanism Evaluation (EME) Project: NIHR129910
Sponsor	Norfolk and Norwich University Hospitals NHS Foundation
	Trust
Contact for Public Queries	[contact]
Contact for Scientific Queries	[name] [name]
	[name]
	[name]
	University of East Anglia
	Norwich Research Park
	Norwich,
	Norfolk
	[name]
	[contact]
Short Title or Acronym	Poly-unsaturated fats for Improving nasal polyps and asthma
	(PUFFIN)
Scientific Title	The efficacy and mechanisms of action of n-3 poly-
	unsaturated fatty acid supplementation in people with non-
	steroidal exacerbated airways disease and uncontrolled
	asthma.
Countries of Recruitment	United Kingdom
Legith Condition(c) or Droblom(c)	Non-staraidal avagarbated airways disaasa
Studied	NOTI-SLEFOIDAL EXACEFDALED AIT WAYS DISEASE
Intervention(s)	Patients will be randomised on a 1:1 basis to receive either
	of the following for 24 weeks;
	ACTIVE ARM:

	6g of Eicosapentaenoic acid (EPA) and Docosahexaenoic acid
	(DHA) in a 1.3:1 ratio; respectively, as six Omega-3 ethyl ester
	90 capsules, taken once daily, or in divided doses, with food.
	or
	CONTROL ARM :
	Matched cansules (six) containing nalm olein IV 56 taken
	once daily, or in divided doces, with food
	once daily, of in divided doses, with lood.
Key Inclusion and Exclusion Criteria	Inclusion Criteria:
	1 Aged >18 years
	2 Diagnosis of N-FRD (non-steroidal anti-inflammatory)
	drug exacerbated respiratory disease) according to
	one of the following.
	i. Positive aspirin challenge plus a history of nasal
	polyposis or asthma.
	ii. More than one typical reaction to NSAIDs or
	aspirin, plus a history of nasal polyposis or
	asthma.
	iii. A single typical reaction to NSAIDs or aspirin and
	a history of nasal polyposis, plus moderate to
	severe asthma.*
	iv. History of nasal polyposis plus asthma, plus
	blood eosinophilia (≥300x10°/L) or raised FeNO
	(>25ppb) within the last 12 months, plus urinary
	leukotriene E4/creatinine >800pg/mg.
	3. Astrima control questionnaire (ACQ) mean score of
	more than 1.5, as this indicates poor control. This is
	requirement to alter medication
	A Stable disease as evidenced by a lack of change in

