6.4.1.2 Treatment Schedule

Participants will be asked to take six grams (as 6 x 1g capsules) once daily or in divided doses, with food.

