6.4.1.4 Dose Modifications, Interruptions and Discontinuations

If a participant forgets to take a dose and it is more than 24 hours after their scheduled dose, they should omit the missed dose and take the next dose when it is due. Participants must not take a double dose to make up for a forgotten dose. Interruptions should be avoided where possible, any reported should be recorded on the eCRF. Participants unable to continue with the IMP due to adverse reaction

or intolerability may reduce to four grams (as 4 x 1g capsules) per day. They must discuss this decision with the site research team and the date of reduction needs to be recorded in the eCRF.

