6.10.4.3 Additional Analyses

Adjusted analyses will be undertaken for the outcomes by adjusting for the baseline value of the respective outcome measure. The primary analysis will be that adjusting for baseline.

Additional adjusted analyses may be undertaken for factors known to be associated with the outcome as decided by the TMG prior to analysis.

A sensitivity analysis will be undertaken based on those with a RBC EPA+DHA enrichment of 2.7-fold.

Further exploratory analyses maybe undertaken, but these will be detailed in the SAP prior to analysis.

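### The 2.7-fold red-cell cut-off labelled as 75% adherence lies below the protocol's own 4 g prediction, so it marks less than 67% of the 6 g schedule

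*Protocol*

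**What the plan says.** Section 6.10.1, item 8, uses red blood cell (RBC) fatty acids to assess adherence. It gives one reference figure: "For the RBC an increase of approximately 3.2-fold would be predicted following a 4g Omega-3 ethyl ester 90 dose". The next sentence sets the threshold: "For the sensitivity analysis a 75% adherence cut-off will be used which equates to an RBC EPA+DHA enrichment of 2.7-fold". The protocol does not show how 2.7 was obtained and gives no prediction for 6 g.

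Section 6.10.4.3 then puts the threshold to use: "A sensitivity analysis will be undertaken based on those with a RBC EPA+DHA enrichment of 2.7-fold". It does not repeat the 75% label.

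For the active arm, section 6.4.1.2 says: "Participants will be asked to take six grams (as 6 x 1g capsules) once daily or in divided doses, with food". The structured summary (section 1.3) identifies these capsules as Omega-3 ethyl ester 90, the same product as in the 4 g reference. Section 6.4.1.4 permits a lower intake only for participants who cannot continue because of an adverse reaction "or intolerability may reduce to four grams (as 4 x 1g capsules) per day".

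**The concern.** The reference enrichment belongs to 4 g and the schedule is 6 g, yet nothing in the protocol carries the threshold from one dose to the other. A participant at 75% of schedule takes more than 4 g, so the predicted enrichment should not be lower than the 4 g figure. The stated cut-off is lower.

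What is at stake is the meaning of one pre-specified sensitivity analysis. If the threshold admits people who took well under 75% of their capsules, the set is diluted relative to its label and the result will be described as something it is not. It may also stand beside a pill-count analysis defined at 80% (section 6.10.4.4). A reader would take the two thresholds as near neighbours, although they may mark quite different levels of intake.

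**Working it through.** **Inputs**
- Predicted RBC enrichment at 4 g: about 3.2-fold (6.10.1, item 8).
- Cut-off: 2.7-fold, said to equal 75% adherence (6.10.1, item 8; used in 6.10.4.3).
- Schedule: 6 g a day (1.3 and 6.4.1.2). Permitted reduction: 4 g a day (6.4.1.4).
- Assumptions: both fold figures are ratios to baseline for the same quantity, and enrichment does not fall as dose rises.

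**Step 1: reproducing 2.7.** With baseline set to 1 and the rise proportional to dose, 75% of the 4 g rise gives 1 + 0.75 × (3.2 − 1) = 2.65, which rounds to 2.7. Other simple rules do not give 2.7:
- proportion of the fold itself: 0.75 × 3.2 = 2.40
- log scale: 3.2^0.75 = 2.39
- 75% of 6 g, linear: 3.48
- 75% of 6 g, log-linear: 3.2^(1.5 × 0.75) = 3.70

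A 4 g basis is therefore the likely origin, but it is inferred.

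**Step 2: the check that needs no curve.** 75% of 6 g is 0.75 × 6 = 4.5 g, which exceeds 4 g. If enrichment does not fall with dose, 4.5 g predicts at least 3.2-fold. Even a complete plateau from 4 g upwards gives 3.2, not 2.7. Conversely, 2.7 is below the 4 g prediction, so the dose that yields it is below 4 g, which is less than 4/6 = 66.7% of the schedule. As an illustration, someone taking four of six capsules every day is at 67% adherence and is predicted to reach 3.2-fold, so clears 2.7 with room to spare.

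**Step 3: size under the linear rule of step 1.**
- Full 6 g: 1 + 2.2 × 6/4 = 4.3-fold.
- 75% of 6 g: 1 + 0.75 × 3.3 = 3.475, about 3.5-fold.
- Dose at 2.7-fold: 4 × (2.7 − 1)/2.2 = 3.09 g, and 3.09/6 = 51.5%. With the unrounded 2.65 it is 3.0 g, or 50%.

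**Step 4: size under other assumed curves through the 4 g point.** The protocol gives no dose-response, so these show a range only.

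| Assumed curve | Fold at 75% of 6 g | Adherence at 2.7-fold |
|---|---|---|
| Saturating, ED50 2 g | 3.28 | 35% |
| Saturating, ED50 8 g | 3.38 | 46% |
| Saturating, ED50 100 g | 3.46 | 51% |
| Linear | 3.48 | 52% |
| Log-linear | 3.70 | 57% |

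**Step 5: the reduced schedule.** Against 4 g, 2.7-fold corresponds to 3.09/4 = 77% under the linear rule (75% with 2.65). The stated equivalence therefore holds for the permitted four-capsule schedule, not for the six-capsule one.

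**The case against.** The strongest reply is that the protocol never says where 2.7 comes from, and the source of the 3.2-fold figure cannot be consulted here. A 6 g prediction of 3.6-fold, for instance, would give 0.75 × 3.6 = 2.70. This stands against any claim that the 4 g origin is proven. It does not rescue the equivalence: that route still puts 4.5 g at 2.7-fold, below the protocol's own 3.2-fold at 4 g.

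Next, the two sentences may not measure the same thing. The first names no fatty acid and no duration; the second names EPA+DHA. Reading both figures as amounts added to baseline still leaves 2.7 at 2.7/4.8 = 56% of 6 g under linearity. A mixed reading could fit: if 3.2 is a ratio but 2.7 is an added amount (3.7 times baseline), the log-linear value of 3.70 at 4.5 g agrees. That requires two adjacent sentences to use different measures, which nothing in the text indicates. The same-measure assumption is the natural reading, but it should be stated as one.

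Third, the cut-off may have been set deliberately for the lowest permitted intake, since it is about 75% of 4 g. The protocol does not say so. It treats four capsules as a reduction for intolerance, and neither section limits the cut-off to that group. What does stand is that simply raising the threshold to 3.5-fold would class a fully compliant four-capsule participant, predicted at 3.2-fold, as non-adherent.

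Last, section 6.10.4.3 defines its set by enrichment alone, and a full statistical analysis plan is due before analysis (section 6.10.4.2). The analysis can therefore be run as written. But the protocol already fixes the adherence meaning of the number, and that meaning conflicts with its own figures, so this is a misstatement and not a detail left for later.

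**Conclusion.** The point holds in a bounded form. On the protocol's own figures, 2.7-fold cannot represent 75% adherence to a 6 g schedule; it represents less than 67%. That bound rests on two assumptions only: a common fold measure, and enrichment that does not fall with dose. The label is then too high by at least 75 − 66.7 = 8.3 percentage points. Under the linear rule the gap is 75 − 51.5 = 23.5 points; across the curves tried it is about 18 to 40 points.

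A reader might infer that the cut-off has been shown to equal 50% adherence, or that 3.5-fold is the correct replacement. Both depend on linearity, which the protocol does not state. A reader might also infer that the trial's main conclusions are at risk. They are not: the intention-to-treat analysis and the 80% pill-count analysis do not use this threshold. Severity is moderate, confined to the RBC sensitivity analysis.

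**What to change.** Reconcile sections 6.10.1 (item 8) and 6.10.4.3 with sections 1.3, 6.4.1.2 and 6.4.1.4, and state how the cut-off is derived, including the fold measure used. Two routes are open:

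1. Re-derive the RBC cut-off for the scheduled dose. It would be at least 3.2-fold, and about 3.5-fold if a linear rule is adopted and stated. The cost is a smaller adherent set and less precision in that analysis.
2. Keep 2.7-fold and restate the adherence it represents: below 67% of the 6 g schedule, with any sharper figure tied to a named dose-response assumption. The cost is a weaker adherence claim; the set does not change.

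In either case, say how participants on the permitted four-capsule schedule are classified, since one threshold cannot mean 75% of both 4 g and 6 g. The work is a change to one number or its label in two protocol sections, carried into the statistical analysis plan before any data are analysed. It implies no view on the dose itself.
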